The **Safety Population** will include all subjects who have received one dose of leronlimab (PRO 140). This population will be used for the analysis of safety parameters or measurements.

Name of Sponsor/Company: CytoDyn, Inc.	
Name of Study Product: leronlimab (PRO 140) - Humanized monoclonal antibody to CCR5	
Protocol Number: CD07_TNBC	Indication: Metastatic Triple Negative Metastatic Breast Cancer (mTNBC)
Statistical Methodology: Adverse events will be coded using the most recent version of MedDRA. TEAEs will be summarized by study phase, cohort, System Organ Class, and preferred term. Safety is reviewed regularly by a DSMB. PFS will be calculated using Kaplan-Meier curves and the median PFS will be read from this curve. Response rates (overall response rate, clinical benefit rate) will be calculated using proportions and 95% confidence intervals. Time to new metastases and overall survival will also be analyzed using Kaplan-Meier curves. Exploratory serial blood markers will be related to PFS using Cox regression, and to response using logistic regression.	

TABLE OF CONTENTS

PROTOCOL SYNOPSIS	5
TABLE OF CONTENTS	17
List of Tables.....	23
List of Figures	24
List of Abbreviations.....	24
1 INTRODUCTION AND BACKGROUND.....	28
1.1 Statement of Intent	28
1.2 Background of the Disease.....	28
1.2.1. Triple Negative Breast Cancer (TNBC)	28
1.2.2. C-C Chemokine Receptor Type-5 (CCR5)	28
1.2.3. Circulating Tumor Cells (CTCs) in Metastatic Breast Cancer (MBC)	31
1.2.4. CCR5+ tumor-infiltrating leukocytes.....	31
1.3 Study Treatments.....	34
1.3.1. Leronlimab (PRO 140).....	34
1.3.2. Carboplatin	35
1.4 Pre-Clinical Studies of leronlimab (PRO 140).....	36
1.4.1. Effect of PRO140 on human CCR5 in breast cancer cells, MDA-MB-231.....	36
1.4.1.1 PRO140 binding to human CCR5 in human breast cancer cells.....	36
1.4.1.2 PRO140 blocks human CCR5 mediated signaling in human breast cancer cells.	37
1.4.1.3 PRO140 blocks human CCR5 mediated invasion of extracellular matrix in human breast cancer cells.....	38
1.4.2. Effect of PRO 140 on Growth of SW480 Human Colon Carcinoma Xenografts	40
1.4.3. Clinical Studies with leronlimab (PRO 140).....	43
1.4.4. PRO 140 1101 Study	43
1.4.5. PRO 140 1102 Study	43
1.4.6. PRO 140 1103 Study	44
1.4.7. PRO 140 1302 Study	44
1.4.8. PRO 140 2301 Study	44
1.4.9. PRO 140 2101 Study	45

1.4.10.	PRO 140_CD01 Study	45
1.4.11.	PRO 140_CD01 Extension Study	46
1.4.12.	PRO 140_CD02 Study	47
1.4.13.	PRO 140_CD02 Extension Study	48

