The final decision on the MTD will be made following a review of the study data by the DSMB. Continuation into Phase II of the study will take place after the DSMB meeting.

Once the MTD has been determined, subjects enrolled in lower dose cohorts will be allowed to escalate the dose to the MTD, if acceptable per the Investigator's discretion.

Phase II

Phase II is a single arm study with 30 patients in order to test the hypothesis that the combination of carboplatin AUC 5 intravenously and MTD of leronlimab (PRO 140) SC will increase PFS in patients with CCR5 + mTNBC. PFS in patients with newly recurred TNBC is approximately 5 months.

Leronlimab (PRO 140) will be administered subcutaneously at a weekly MTD dose determined in the Phase Ib portion of the study and carboplatin target of AUC 5 every 3 weeks as combination therapy until disease progression or intolerable toxicity. A de-escalation dose of carboplatin will be allowed based on the toxicity, efficacy evaluation, and clinical judgment by physician.

In both the Phase Ib and Phase II portions of the study, patients will be evaluated for response at the end of 2 cycles (i.e., every 6 weeks) for the first 6 cycles (18 weeks) and at end of 3 cycles (i.e., every 9 weeks) thereafter and at EOT by CT, PET/CT or MRI with contrast (per treating investigator's discretion) using the same method as at baseline. Tumor measurements will be done using RECIST v1.1.

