6.1.5. Leronlimab (PRO 140) - Dose Modifications

The dose interruption, reduction, and permanent discontinuation for any toxicity are described below.

Dose interruption: Refer to [Table 6-3](#) below. Recovery to acceptable levels must occur to allow leronlimab (PRO 140) continuation. Any adverse event deemed to be related to leronlimab (PRO 140) that requires a dose hold of more than 21 days will result in permanent discontinuation of leronlimab (PRO 140).

Table 6-3: Leronlimab (PRO 140) Dose Modification and Management for Injection Site Reactions

CTCAE Grade	Treatment Modifications
Grade 1	No dose adjustment is required.
Grade 2	First Occurrence: No dose adjustment is required. Second Occurrence of the same event: Closely follow-up for resolution of the AE to Grade ≤ 1
Grade 3	Withhold treatment until symptoms resolve to: • Grade 1 or less
Grade 4	Study treatment will be permanently discontinued
Dose Limiting Toxicities (DLT) as outlined under Section 3 (Study Design)	Study treatment will be permanently discontinued

Note:

- *If Grade 3 event meets the DLT criteria: Study treatment will be permanently discontinued*
- *If Grade 3 event does not meet the DLT criteria: Study treatment will be withheld until symptoms resolve to Grade 1 or less before administering the next dose.*

Dose Modification: If a dose-response relationship for toxicity is observed, a reduced dose can be given to the subject. Dose adjustments will be allowed based on the toxicity, efficacy evaluation, and clinical judgment by physician.

- **Cohort B (PRO 140 525 mg):**

Dose de-escalation: If a dose-response relationship for toxicity is observed at leronlimab (PRO 140) 525 mg dose, the dose can be de-escalated to 350 mg. If no toxicity is observed at reduced dose (350 mg), the subjects will receive the reduced dose until disease progression, consent withdraw or death. No more dose de-escalation will be allowed if another toxicity event is observed at reduced dose level.

- **Cohort C (PRO 140 700 mg):**

Dose de-escalation: If a dose-response relationship for toxicity is observed at leronlimab (PRO 140) 700 mg dose, the dose can be de-escalated to 525 mg. If no toxicity is observed at reduced dose (525 mg), the subjects will receive the reduced dose until disease progression, consent withdraw or death. One more dose de-escalation (to 350 mg) will be allowed as per discretion of the treating physician.

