6.2.13. Carboplatin - Toxicity Management & Dose Delays/Modifications

The dose interruption, reduction, and permanent discontinuation for any toxicity are described below.

Dose interruption: Refer to table below. Recovery to acceptable levels must occur to allow carboplatin continuation.

Table 6-4: Carboplatin Dose Modification and Management

Toxicity	Grade/Description	Carboplatin
Hematologic Toxicities		
Thrombocytopenia	Grade 1	Maintain dose level.
	Grade 2	Hold dose & follow CBC weekly. Once \leq Grade 1 (platelets \geq 75,000/mm ³), resume at same dose.
	Grade 3	Dose reduction to AUC 4
	Grade 4	Permanently discontinue Carboplatin
Neutropenia	Grade 1 , 2 or 3 without fever	Maintain dose level.
	Grade 3 w/ fever or Grade 4	1st occurrence: Hold dose & follow CBC weekly. Once resolved to $> 1.0 \times 10^9/L$ (if neutropenia was the only toxicity noted), resume at same dose. If other toxicity was noted, resume with AUC 4. 2nd occurrence: Discontinue Carboplatin
Non-Hematologic Toxicities		
Allergic reaction or hypersensitivity	\leq Grade 3	Hold dose until resolved to \leq Grade 1 & then resume at same dose level.
	Grade 4	Permanently discontinue Carboplatin

Toxicity	Grade/Description	Carboplatin
Infection	Grade 1 or 2	Hold dose until systemic treatment for infection is complete. If no neutropenia, resume at same dose level. If neutropenic, follow instructions above (hematologic section). If no resolution after > 3 weeks: permanently discontinue Carboplatin
	Grade 3	Discontinue Carboplatin
Herpes zoster or simplex	Any grade	Hold dose until lesions are dry & then resume at same dose level.
Neuropathy	Grade 2 w/pain or Grade 3	Hold dose until resolved to \leq Grade 2 or baseline then resume at AUC 4. May continue on single-agent leronlimab (PRO 140) (per treating investigator's discretion)
	Grade 4	Permanently discontinue Carboplatin
Renal dysfunction	CrCl \leq 15 mL/min	Hold dose until CrCl $>$ 15 mL/min & then resume.

Note: Patients who discontinue carboplatin for any reason will be allowed to continue to receive leronlimab (PRO 140) per treating investigator's discretion. In such cases, patients will be re-consented so that they are appropriately informed of other treatment options that have demonstrated improvement in clinical outcomes.

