8.7.3.2 Safety Analyses

Safety will be assessed by close monitoring and timely assessment of adverse events (AEs), laboratory parameters (blood tests, urinalysis), vital signs (blood pressure, heart rate), subject's medical condition (physical examination including weight), general well-being and activities of daily life (Eastern Cooperative Oncology Group (ECOG) performance status). Each subject will be regularly assessed in each cycle for potential AEs and disease related signs and symptoms. The CTCAE v5.0 will be used to grade toxicities / AEs.

The Safety population will be used for the analysis of safety endpoints.

Descriptive statistics (n, mean, standard deviation, median, minimum, and maximum) will be calculated for continuous variables. Frequencies and percentages will be presented for categorical variables.

Adverse Events:

Adverse events will be coded using the most recent version of Medical Dictionary for Regulatory Activities (MedDRA). Treatment Emergent AE's (TEAE) are defined as events with an onset on or after the first treatment. TEAEs will be summarized by study phase, treatment group, System Organ Class, and preferred term. The following TEAE summaries will be provided:

- Overall (i.e., regardless of severity or relationship to treatment)
- By severity grade (mild, moderate, severe, or life threatening for SAEs)
- By relationship to clinical trial treatment according to the mapping scheme below:
 - Potentially related: will include all adverse events with a relationship rating of “definitely”, “probably” or “possibly”.
 - Unlikely/not related: will include all adverse events with a relationship rating of “unlikely” or “unrelated”.

In addition, separate summaries of serious adverse events, and adverse events resulting in discontinuation of study treatment will be presented.

Clinical Laboratory Data

All laboratory values will be listed. Laboratory measurements will also be summarized as continuous variable and presented by treatment group and time point.

Physical Examination

All physical examination findings will be listed and/or summarized.

Vital Signs

All vital sign findings will be listed and summarized.

Electrocardiograms (ECGs)

All ECG findings will be listed and summarized.

Eastern Cooperative Oncology Group (ECOG) performance status

All ECOG performance status findings will be listed and summarized.

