9.2.1. Impact on Study Treatment

The impact the event had on the study treatment will be assessed as either: none, study treatment interrupted, study treatment discontinued, or not applicable. The “not applicable” assessment will be used only when the subject is no longer in the treatment period of the protocol or died.

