8.4.1 Adverse Events

Adverse events will be classified by system organ class (SOC) and preferred term (PT) according to the most recent version of MedDRA dictionary.

TEAE are defined as adverse events with onset date on or after the first treatment. TEAEs will be summarized by treatment group, System Organ Class, and preferred term. The following TEAE summaries will be provided:

- a) Overall (i.e., regardless of severity or relationship to treatment)
- b) By severity grade
- c) By relationship to clinical trial treatment

Unless otherwise specified, at each level of subject summarization, a subject will be counted only once. If there is more than one occurrence of an event, the event of the worst severity or the worst-case relationship category will be summarized.

AEs leading to premature discontinuation of clinical trial treatment and Serious Adverse Events (SAEs) will also be summarized by treatment group and relationship.

All adverse events recorded in the eCRF will be presented as by-subject listings.

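### Leronlimab dose can change within a patient, but adverse events are tabulated by cohort or fixed-dose group with no dose-at-onset rule, and the action-taken item cannot show a reduction or which drug was stopped

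*SAP*

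**What the plan says.** **Dose changes.** Protocol section 3 provides that, once the MTD is set, "subjects enrolled in lower dose cohorts will be allowed to escalate the dose to the MTD", subject to the investigator's judgment. SAP 2.1 repeats this. Protocol 6.1.5 also allows reductions: for Cohort B "the dose can be de-escalated to 350 mg", and for Cohort C "the dose can be de-escalated to 525 mg" with one further step to 350 mg.

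**Adverse event tables.** Three rules appear:

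- Protocol synopsis, Statistical Methodology: "TEAEs will be summarized by study phase, cohort, System Organ Class, and preferred term".
- Protocol 8.7.3.2: "TEAEs will be summarized by study phase, treatment group, System Organ Class, and preferred term".
- SAP 8.4.1: "TEAEs will be summarized by treatment group, System Organ Class, and preferred term". Study phase is gone.

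Protocol 8.1 defines the treatment groups as three fixed leronlimab doses with carboplatin AUC 5, and only for the dose-finding portion. SAP 8.4.1 counts a subject once at each level of summary, at the worst severity or relationship.

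**Action taken.** Protocol 9.2.1 records the impact of an event on study treatment as "none, study treatment interrupted, study treatment discontinued, or not applicable". Carboplatin can be reduced to AUC 4, and it can be stopped while leronlimab continues (Protocol 6.2.13). SAP 8.4.1 summarizes events leading to premature discontinuation of trial treatment without separating the drugs.

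**The concern.** A table by cohort describes the toxicity of a dose only while patients stay on that dose. Here a patient who starts at 350 mg may spend much of the treatment period at the MTD. If a Grade 3 event then occurs, the by-cohort table shows it in the 350 mg row.

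Safety and tolerability form part of the Phase Ib primary objective. The Phase Ib secondary endpoint counts adverse events from first treatment until 12 weeks after completion, so it includes time after a switch. The SAP tables for laboratory values, vital signs, ECG and physical examination use treatment group too, and so share the gap.

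The action-taken item raises a different problem. It loses the nature of the action and the drug concerned. It does not itself place an event under a wrong dose; the grouping rule does that.

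**Working it through.** **1. The plan's own figure.** Three dose levels (Protocol section 3) with at most six patients each give 3 × 6 = 18, the stated Phase Ib maximum. It reproduces.

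**2. How many patients could move up.** Under the 3+3 rules, a cohort below the MTD grows from three to six only after a DLT, and escalation continues only if exactly one of the six has a DLT. The MTD level is filled to six.

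- MTD 700 mg, no DLTs: 3 + 3 + 6 = 12 treated; 3 + 3 = 6 could move up, half of those treated.
- MTD 700 mg, Cohorts A and B both expanded: each holds one DLT patient. If these stop permanently, as the DLT row of Table 6-3 says, (6 − 1) + (6 − 1) = 10 of 18 could move up.
- MTD 525 mg: only Cohort A can move up, so 3, or 6 − 1 = 5.

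These are ceilings. A patient must still be on treatment and the investigator must agree.

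**3. Weight of one event.** 1/6 = 17 percentage points; 1/3 = 33 percentage points.

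**4. Illustration of the flattening (assumptions, not plan figures).** Time on treatment is taken as exponential with a median of 5 months, borrowing the PFS figure in Protocol section 3. The patient starts in Cohort A at week 0 and moves to 700 mg at time t if still on treatment.

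- λ = ln 2 / 5 = 0.1386 per month; t in months = weeks × 12/52.
- Share of treatment time after the switch: s = exp(−λt).
- With a true 700:350 event rate ratio r = 2, the ratio seen when all Cohort A time is charged to 350 mg is r / [(1 − s) + r·s].
- With an assumed event rate h = 0.05 per month at 350 mg, the proportion of patients with an event is h/(h + λ) = 26.5% if all treatment is at 350 mg, and 2h/(2h + λ) = 41.9% if all is at 700 mg. With a switch at t it is [h/(h + λ)]·(1 − e) + e·[2h/(2h + λ)], where e = exp(−(h + λ)t).

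| Switch at week | s | Ratio seen (true 2) | Shown under 350 mg (true 26.5%) |
|---|---|---|---|
| 9 | 75% | 1.14 | 36.9% |
| 12 | 68% | 1.19 | 35.6% |
| 18 | 56% | 1.28 | 33.5% |
| 39 | 29% | 1.55 | 29.3% |

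Week 9 is three back-to-back 3-week DLT windows. Week 12 adds the second three patients at 700 mg. Week 18 is six windows (every cohort expanded). Week 39 stands for slow accrual. With h of 0.02 or 0.10 and r of 1.5 or 3, the 350 mg figure always falls between the two true values. For r = 1.5 the ratio seen runs from 1.09 to 1.31, and for r = 3 from 1.20 to 1.91 (weeks 9 to 39). A shorter time on treatment would reduce s.

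**5. Timing against the MTD decision.** DLTs are counted in Cycle 1 (Protocol 8.7.3.1), and upward moves open only once the MTD is determined. No upward move can enter a DLT count.

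**6. Action taken.** Protocol 6.1.5 and 6.2.13 provide for reducing each drug, but none of the four options in 9.2.1 is a reduction. Protocol 6.2.13 allows one drug to stop alone, but 9.2.1 has one item. A discontinuation table built on it cannot name the drug.

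**The case against.** Several objections have force.

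- **The SAP is silent rather than wrong.** A reader might infer that SAP 8.4.1 itself charges post-switch events to the original cohort. It does not say so: Protocol 8.1 names groups by dose, and the count-once rule does not choose a column. This stands for the treatment-group tables, where the assignment is undefined. It does not rescue the synopsis table, where a cohort is where the patient was enrolled.
- **Dose selection.** A reader might infer that upward switching distorts the MTD or the Phase II dose. Step 5 shows that it cannot.
- **Reversal.** A reader might infer that the dose-toxicity relation could be reversed. In every scenario computed it is only weakened. In cohorts of three to six, chance alone can reorder columns.
- **All 12 of 18.** A reader might infer that every patient in Cohorts A and B could cross. Both reach six only with a DLT in each, and the end of Protocol 6.1.5 stops treatment for a DLT at 350 mg. The count could be 11 rather than 10 if the 525 mg reduction text keeps the Cohort B patient on treatment. Table 6-3 and that text must be reconciled.
- **Phase pooling and miscoding.** A reader might infer that Phase Ib and Phase II patients at the MTD will be pooled, or that reductions will be coded as none or interrupted. No Phase II group is defined and the eCRF is not in the documents, so neither is established. No table of dose reductions is planned either. The term study treatment sometimes means leronlimab alone.
- **Mitigation.** Dosing is listed and summarized (SAP 8.1.5), all events are listed by subject, and dose is a possible risk factor for injection-site reactions (SAP 8.4.2.4). Dose at onset can therefore be derived, but no planned adverse event table uses it.

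**Conclusion.** The point holds for the cumulative descriptive safety tables. Dose can change within a patient in both directions, and no rule ties an event to the dose at its onset. The synopsis table, followed as written, reports post-switch events under the original cohort, and the treatment-group tables leave the matter open. The expected effect is a flatter dose-toxicity relation. Downward moves dilute the higher-dose column in the same way, but the documents give no basis for sizing that.

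If the MTD is 700 mg, up to 6 patients (no DLTs) or about 10 (DLT patients discontinued) could move up. Under the assumed 5-month median time on treatment, 29% to 75% of Cohort A treatment time could fall at another dose. The upper end requires the MTD to be declared on the first three patients at 700 mg; with six there it is 68%.

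Two smaller defects are plain from the text. The SAP drops the study-phase split that the protocol states twice, and 9.2.1 offers no code for a reduction and one item for two drugs. The point should be corrected before database lock; it is no reason to doubt the MTD rule.

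**What to change.** **SAP 8.4.1**

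- Add TEAE tables by leronlimab dose at onset, with exposure time per dose level. Count a subject once in each dose column, at the worst severity in that column, with subjects ever treated at that dose as the denominator.
- Restore study phase and define the Phase II group.
- Keep the assigned-cohort table, limited to time on the assigned dose. Align the synopsis and Protocol 8.7.3.2 with this.

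**Protocol 9.2.1 and the CRF**

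- Record action taken separately for leronlimab and carboplatin: none, interrupted, reduced, discontinued or not applicable.
- Report events leading to discontinuation of leronlimab, of carboplatin, and of both.

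**Cost.** Onset dates and dosing records are already collected, so the tables need only programming; the action-taken item needs a CRF change. A patient can appear in more than one dose column, which a footnote can explain. The figures by dose at onset remain descriptive, because patients who move up are those still on treatment at the lower dose. No dose or clinical rule changes.

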8.4.2 Injection Site Reaction Assessment

Injection Site Reaction Assessment will be presented as by-subject listing and summarized.

All data from the injection site reaction assessments of the repeated subcutaneous administration of PRO 140 will be descriptively summarized.

8.4.2.1 Injection Site Reactions per DAIDS AE Grading

Local injection-site reactions are assessed for each injection including Pain, Erythema, Pruritis, Bleeding and Absorption of drug.

Each injection site reaction is monitored per protocol-defined severity criteria developed in align with the guidelines of (Division of AIDS Table for Grading the Severity of Adult and Pediatric Adverse Events [DAIDS AE Grading Table])

Table 8-1: Injection-site Reactions, DAIDS Grading

Parameter	Grade 1 (Mild)	Grade 2	Grade 3 (Severe)	Grade 4
		(Moderate)		(Potentially life-
				threatening)
Injection-site pain	Pain without	Pain without	Pain without	Pain without
	touching or pain	touching or pain	touching or pain	touching or pain
	when area is	when area is	when area is	when area is
	touched: no or	touched limiting	touched causing	touched causing
	minimal limitation	use of limb OR	inability to perform	inability to perform
	of use of limb	causing greater	usual social and	basic self-care
		than minimal	functional	function OR
		interference with	activities	hospitalization
		usual social and		(other than
		functional		emergency room
		activities		visit) indicated for
				management of
				pain/tenderness
Characterization of	Erythema OR	Erythema OR	Ulceration OR	Necrosis
the injection site, if	induration of 5x5	induration OR	secondary infection	(involving dermis
not normal	cm - 9x9 cm (or 25	Edema > 9 cm any	OR Phlebitis or	and deeper tissue)
	cm2-81 cm2)	diameter (or > 81	Sterile abscess OR	
		cm2)	drainage	
Pruritus associated	Itching localized to	Itching beyond the	Generalized itching	N/A
with injection	injection site AND	injection site but	causing inability to	
	relieved	not generalized OR	perform usual	
	spontaneously or	itching localized to	social and	
	< 48 hours of	injection site	functional	
	treatment	requiring ≥ 48	activities	
		hours treatment		
Bleeding	Initial bleed that	Bleeding that	Continued bleeding	N/A
	does not exceed	exceeds bandage	that requires	
	bandage and	and spontaneously	change of dressing	
	spontaneously	stops	and alternative	
	stops		injection site	

Protocol: CD07_TNBC CytoDyn, Inc.

Parameter	Grade 1 (Mild)	Grade 2	Grade 3 (Severe)	Grade 4
		(Moderate)		(Potentially life-
				threatening)
Absorption of drug	Minor elevation of	Leakage at	Leakage at	
	skin at injection	injection site	injection site that	
	site but no leakage	ceases with	does not cease with	
	of injection	decrease in	decrease in	
	material	injection rate	injection rate	

The grading for all subjects and parameters will be listed. The number and percentage of patients with worst reported DAIDS grade will be summarized regardless of the location of injection (i.e., left or right side) in the abdomen. Each patient will be counted only for the worst grade observed.

In addition, time to onset of the first worst case injection site reaction will be summarized.

Time to onset of worst grade will be summarized for each local injection reaction parameter listed above using Kaplan-Meier method. Median time to onset and 95% C.I will be summarized. In addition, Kaplan-Meier plots will be generated.

8.4.2.2 Systemic manifestations (e.g., hypotension, fever, difficulty breathing) within the post-administration monitoring period

This will be assessed from the vital signs data using the pre and post assessment:

- Hypotension if there is a reduction in SBP of >= 20 mmHg or reduction in DBP of >= 10 mmHg or if post treatment SBP is >= 90mmHg or DBP is <=60mmHg
- Fever if post treatment temperature is $> 40^{\circ}$ C
- Difficulty breathing if increase in Respiratory Rate is > 30%

The subjects with above systemic manifestations will be listed. Shift table for Fever will be presented with counts and percentages of subjects for shift (change) from pre-treatment at T1 to post-treatment at T1. Percentage of subjects with Hypotension or Difficulty breathing post treatment will be summarized.

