- (3) Treatment Period: Subjects who meet the eligibility criteria will have completed following evaluations and assessments before receiving treatment: a) review of medical and medication history; b) physical examination, vital signs and documentation of ECOG performance status; c) ECG; d) routine serum biochemical, hematologic, urine pregnancy (if applicable) and urine laboratory assessments. Additionally, a blood sample will be collected prior to treatment administration for CTCs PD-L1/CCR5, and CTC CAMLs analysis.

Each treatment cycle will consist of 21 days. Leronlimab (PRO 140) will be administered subcutaneously weekly on Days 1, 8, and 15 in combination with carboplatin AUC 5 on Day 1 of each cycle (every 21 days). Day 1 of Cycle 2 begins at Day 22. The study treatment will be administered by a licensed medical professional at clinic site or self-administered by subjects at home.

Subjects will be allowed to continue treatment under subsequent treatment cycles until any one of the following occurs: progressive disease or unacceptable toxicity or withdrawal of consent.

(4) Follow-Up Period: An End of Treatment (EOT) visit will be conducted 30 (\pm 3) days after the last treatment visit (i.e., after last dose of leronlimab (PRO 140) and carboplatin). Additionally, follow-up will be done for survival status, by clinic visits or phone or another method of contact, every 3 months (\pm 1 month) for 2 years after treatment discontinuation or until death, whichever occurs first.

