7.9.3 Time to event

Time to event will be calculated according to the formula noted below:

Time to event = (Date of Event
$$-$$
 Date of first treatment) + 1

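### SAP 8.4.2.1 applies Kaplan-Meier to time to each patient's own worst injection-site grade, which is not the onset of any single outcome and can, though need not, lengthen as tolerability worsens

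*SAP*

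**What the plan says.** SAP 8.4.2.1 grades five local reaction parameters (pain, appearance of the site, itching, bleeding, drug absorption) on a DAIDS-based scale. It lists all grades and tabulates patients by worst grade: "Each patient will be counted only for the worst grade observed". It then adds two timing outputs. One is general: "In addition, time to onset of the first worst case injection site reaction will be summarized". The other is by parameter: "Time to onset of worst grade will be summarized for each local injection reaction parameter listed above using Kaplan-Meier method". The reporting is then set: "Median time to onset and 95% C.I will be summarized", plus plots.

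SAP 7.9.3 counts time from first treatment, with one day added. Dosing under SAP 2.1 is "subcutaneously weekly on Days 1, 8, and 15 in combination with carboplatin AUC 5 on Day 1 of each cycle", and it is open-ended: "Subjects will be allowed to continue treatment under subsequent treatment cycles until any one of the following occurs" (progression, unacceptable toxicity or withdrawal of consent).

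For this output the SAP gives no grade threshold, no time to first reaction, and no censoring rule for patients without a reaction or still on treatment. SAP 7.4 rules out sensitivity analyses. SAP 8.4 says that safety analyses carry no inference.

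**The concern.** A time-to-event curve is readable when the event means the same thing in every patient. Here it is Grade 1 in one patient and Grade 3 in another. An early Grade 1 reaction counts as the event only if nothing worse follows. If a Grade 2 reaction comes later, the event moves to that date. The phrase "time to onset of the first worst case injection site reaction will be summarized" does not cure this, because it only picks the first occurrence of the patient's own maximum.

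Two consequences follow. A patient who reacts early and later reacts more severely is recorded with a later onset than one who reacts early and never gets worse. And more weeks on treatment mean more chances of a new maximum, so the time can lengthen with no change in the risk per injection.

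Injection-site reactions are adverse events of special interest (Protocol 9.2.6), so a median labelled as time to onset is likely to be read as a tolerability result.

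**Working it through.** The plan states no figure for this output, so there is none to reproduce. Dosing frequency, time origin and the event definition come from the SAP sections above. Reaction rates and treatment duration are assumptions.

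**1. Counterexample, no rates needed.** Take 30 patients per group. An event on Day 8 gives (8 − 1) + 1 = 8 days.
- Group A: all have Grade 1 on Day 8 and nothing worse. Planned median: day 8.
- Group B: the same, but 20 of 30 also have Grade 3 on Day 64. Event times are day 8 in 10 patients and day 64 in 20. After day 8 the curve stands at 20/30 = 0.67, so the planned median is day 64.

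Group B is strictly worse and shows later onset. With the event fixed in advance, time to first reaction of any grade has median day 8 in both groups. Time to first Grade 3 or higher is not reached in A and is day 64 in B, which is the right order.

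**2. Range of assumed rates.** Weekly injections, independent grades at each injection, exponential treatment duration with median 5 months, censoring at the last assessment, 20,000 simulated patients per setting. Kaplan-Meier median time to own worst grade, in weeks (first injection = week 1):

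| Grade 1 per injection | Assessment | Grade 2 at 0% | 2% | 5% |
|---|---|---|---|---|
| 30% | every injection | 2 | 4 | 5 |
| 10% | every injection | 7 | 9 | 8 |
| 5% | every injection | 14 | 14 | 10 |
| 30% | clinic only | 2 | 3 | 3 |
| 10% | clinic only | 13 | 13 | 10 |
| 5% | clinic only | 34 | 25 | 16 |

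The clinic-only rows reflect Protocol Table 4-1, footnote 19: home injections have no injection-site assessment, and Day 8 and Day 15 injections after Cycle 1 may be given at home. They assume that all of those are given at home, which is the extreme case.

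The 0% column can be checked by hand, because the worst grade is then always Grade 1 and the median is the first n with (1 − p)^n ≤ 0.5:
- p = 0.30: 0.70² = 0.49, so week 2.
- p = 0.10: 0.90⁶ = 0.53 and 0.90⁷ = 0.48, so week 7.
- p = 0.05: 0.95¹³ = 0.51 and 0.95¹⁴ = 0.49, so week 14.
- Clinic-only assessments fall in weeks 1, 2, 3, 4, 7, 10, 13 and so on. The 2nd is week 2, the 7th is week 13, and the 14th is 4 + 3 × 10 = week 34.

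In the 30% case with every injection assessed, the share of patients with Grade 2 rises from 0% to about 40% and then 62 to 63%, while the planned median lengthens. On the same data, first Grade 1 or higher stays at 2 weeks. First Grade 2 or higher goes from not reached to 34 to 35 weeks and then 14 weeks, so it shortens as it should. In the clinic-only 30% case the Grade 2 share is 0, 21 and 42%.

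**3. Follow-up alone.** With Grade 1 in 30% and Grade 2 in 5% of injections, 30 patients and 2,000 runs, the planned median is day 8, 29 and 57 when all patients are followed for 6, 18 and 36 weeks. The risk per injection is the same throughout.

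**4. Higher Grade 2 rates.** With Grade 1 at 30% and every injection assessed, the planned median falls back to 3 weeks at a Grade 2 rate of 20% and to 2 weeks at 30%. The measure is therefore not monotone in tolerability.

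**The case against.** The strongest reply has four parts.

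- **The reversal depends on the rates.** This stands. It appears when mild reactions are common and worse ones uncommon. It is absent at a 5% Grade 1 rate, and it shrinks to one week in the 30% case when home injections go unassessed. A reader might infer that worse tolerability generally shows as later onset. The documents give no rates that would support that. The simulation also leaves out any withholding or stopping of injections after severe reactions.
- **No comparison is planned.** A reader might infer that the flaw spoils a dose or phase comparison. SAP 8.4.2.1 plans none for this output. SAP 8.4.2.4 names dose as a possible risk factor for reactions but does not tie it to these curves.
- **Severity remains visible.** This also stands. The listing of all grades, the worst-grade table and the adverse event summaries show severe reactions whatever the curve looks like.
- **Each patient's maximum is known at database lock, and when the worst reaction occurs is a fair descriptive question.** Partly right. The quantity can be computed, and Kaplan-Meier is not ruled out merely because the event is identified in hindsight. What remains is interpretation: with unequal, open-ended follow-up and an event whose grade varies between patients, the curve has no single outcome behind it.

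**Conclusion.** The concern holds as a point of interpretation about a secondary safety display. As written, the median, confidence interval and plot mix grades, depend on treatment duration, and can move in either direction as tolerability worsens. The counterexample proves the possibility from the SAP's definition alone. The sizes in weeks rest on assumed rates, independence between injections and an assumed treatment duration. In the settings tabulated, raising the Grade 2 rate from 0 to 5% moved the median from 3 weeks later (2 to 5) to 18 weeks earlier (34 to 16).

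The documents do not support a reading that severe reactions would be concealed or that trial decisions are at risk. The output is descriptive, and dose escalation, the MTD and all efficacy analyses are defined without it. This is a worthwhile correction of low severity.

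**What to change.** In SAP 8.4.2.1, replace the Kaplan-Meier time to worst grade with two outputs per reaction parameter: time from first injection to the first reaction of Grade 1 or higher, and to the first of Grade 2 or higher. Censor patients without the event at their last clinic injection-site assessment, and note that home injections are not assessed. Reword the general sentence on the first worst-case reaction to match.

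Keep the worst-grade frequency table. If the timing of the worst reaction is still wanted, give it as a simple descriptive summary among patients who had a reaction, not as a Kaplan-Meier estimate.

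The cost is about two SAP sentences and the matching table shells. The data already being collected and the planned software suffice.
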